The intervention will be tailored on the current substance use status of each participant (see Figure 1). Computer software can easily deliver such a bifurcated treatment approach –

such an intervention design is consistent with evidence that motivational approaches may work best with less motivated individuals. The intervention will contain language referring to either substance use in general (past or present behaviors and beliefs) or current substance use, and will not assume current substance use. For women who state that they have already quit (see “No” in Figure 1), the three-dimensional animated narrator will present a section that will focus on how they can remain abstinent now and after they leave the shelter (Relapse Prevention). An example in this section will include if the woman decides to return to her abuser, how avoiding using with her abuser could decrease her risk for abuse and for subsequent substance use. These women (i.e., those who have already quit) will have the option to create a personalized **Safety Plan**, and can select from a menu of potential personal change goals (i.e., maintain their change) and/or optionally, they can enter their own change goals in free text.

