Women who endorse current substance use will be asked about their interest/readiness in quitting their substance use (“Ready to Quit?”) leading to a bifurcated treatment response such that those participants reporting a goal of immediate abstinence will move more quickly to a section consistent with primary goal-setting for substance use reduction. This arm will follow closely the guidelines established in previous intervention studies which will include components of a quit contract and will assist the woman in identifying specific goals and a timeline for reaching these goals. These participants will have the option to create a personalized **Safety Plan** that will include the specific goals that the women have identified and/or optionally, can enter their own change goals in free text. Some example of goals will include attending AA or NA, attending substance use treatment, speaking to shelter staff about coordinating substance use treatment, planning for support groups after leaving the shelter such as IPV support groups. For the remaining participants who report not being ready to quit at this time, the narrator will present sections including **pros and cons, feedback, and optional goal-setting**. Specifically, in the pros and cons section, the narrator will normalize feelings of ambivalence about substance use, noting that most people can identify sides to their use that are both positive and negative. For example, the narrator will first ask for the good things about substance use and provide a checklist in which the participant endorses as many pros as they would like. The narrator then notes that for many people there are also some “not so good” aspects to substance use, and presents another checklist in which the participant endorses as many cons of substance use as they would like. Then the narrator reflects back to them the specific pros and cons that they selected and notes that feeling two ways about one’s substance use is quite normal. For example, the narrator would say, “You really seem to feel two ways about this. On the one hand, you like the way that smoking marijuana helps you relax when you have reminders of the abuse. But at the same time, it is only a temporary fix for your problems.” In the feedback section, the narrator will first present participants with normative feedback regarding their typical substance use using an easy-to-read graphical display and clear description of what the feedback means. This feedback includes key pieces of information: how much the participant reported using, how much they think most other women use, and how much of it other women actually use. Normative feedback is followed by feedback with the specific negative consequences that the participants reported having experienced as a result of their substance use. The narrator will then elicit brief elaborations of negative consequences using simple questions keyed to each type of consequences. For example, if a woman endorsed the item regarding health problems as a result of substance use, the narrator could ask, “What sorts of health problems have you had?” and provide a checklist of possible response. A follow up question could then ask the participant to choose ways in which their health could be improved if they did decide to make a change. There will be a section that will provide feedback on each participant’s self-reported readiness to change with regard to substance use. In the optional goal-setting section, the narrator will begin by briefly summarizing the state of each participant’s ambivalence regarding her substance use, and the factors pulling her in either direction. The narrator then asks if she would like to set a change goal. If she does not wish to do so, the narrator reflects her lack of readiness at this time and elicits information

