IPV: The Composite Abuse Scale (CAS) is a widely used self-report of behaviors scale with 4 subscales that measure severe, combined abuse, emotional abuse, physical abuse, and harassment. The CAS has recently been published in the Centers for Disease Control and Prevention compendium of intimate partner violence measures. It consists of 30 items presented in a six point format requiring respondents to answer “never”, “only once”, “several times”, “monthly”, “weekly” or “daily” in a twelve month period.

The Cyber Stalking Scale measure is a 6 –item measure and assesses the use of technologies in stalking and harassment.

Safety Behavior Checklist (SBC) has 15 items that assess the use of strategies suggested to keep victim safe (e.g., hiding money and extra clothing).

*Theorized Mediators: The Confidence Ladder* will be used to assess the participants’ levels of confidence regarding their ability (self-efficacy) to change and abstain from substances. *Readiness Ruler* will be used to assess the degree to which participants’ are ready to cut down or quit alcohol or drugs.

Women who participated in the SHE intervention will complete a computer-based measure at the 3- and 6-month follow-up assessment to determine the extent to which participants achieved their goals on their personalized plan; an indication of the degree to which the SHE intervention had an impact on behavioral change. This measure will follow a similar format to the Effectiveness in Obtaining Resources Scale, which assesses battered women’s effectiveness in obtaining various resources.

At follow up, if a participant is unable to meet in-person to complete the assessments (e.g. participant has moved out of state), she will be given the option of participating in the assessment over the phone. Phone sessions will consist of the research assistant administering all the follow up assessments listed above via a phone session, with the exception of breathalyzer, urine, and hair sample testing.

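### Goal attainment, recorded only in SHE women on goals they choose themselves, cannot indicate the impact of SHE; the Protocol should relabel it as a descriptive process measure (minor)

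*Protocol*

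**What the plan says.** **The measure.** Under Measures, the Protocol states: "Women who participated in the SHE intervention will complete a computer-based measure at the 3- and 6-month follow-up assessment". Its purpose is "to determine the extent to which participants achieved their goals on their personalized plan", and the result is to be read as "an indication of the degree to which the SHE intervention had an impact on behavioral change".

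**Where the goals come from (Study Procedure).** A woman who has already quit "can select from a menu of potential personal change goals (i.e., maintain their change"), and "optionally, they can enter their own change goals in free text". For women who want to quit now: "Some example of goals will include attending AA or NA, attending substance use treatment, speaking to shelter staff about coordinating substance use treatment". For women not ready to quit: "The narrator then asks if she would like to set a change goal". A woman in this branch may decline to set one. Making a plan is optional in every branch, and the plan can be revised at the booster session.

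**The control arm.** Controls watch entertainment videos (Methods - Randomized Pilot Trial; Control condition). Study Procedure says that this content does not overlap with SHE.

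**Care common to both arms.** All women keep usual shelter care, with no referral or counselling withheld (text under Figure 2), and all receive a list of treatment and community resources (Potential benefits).

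**Planned analyses.** Data Analysis and the SAP plan effect sizes with 95% confidence intervals for using days, days of substance use services and severity of partner violence, with adjustment for baseline. The goal measure does not appear in the aims, Table 1, Data Analysis or the SAP.

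**The concern.** The clause in Measures attributes an observed level of goal attainment to SHE. Attribution needs a comparison, and this quantity has none. There is no control value, because controls make no plan. There is no baseline value, because the goals are first set during the intervention session. The goals are also self-chosen. Some resemble what shelter care and the shared resource list already encourage, and one option is to keep up a change made before the session.

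What is at stake is one statement in the pilot report. The sentence in Measures is the only text that tells the reader how to interpret the result, and no analysis section qualifies it. Followed as written, it would let any level of attainment above zero be described as some degree of SHE impact. Pilot results are to support the application for a larger trial (Phase III Refinement of SHE). Between-arm estimates from about 20 to 21 women per condition will be imprecise, so a favourable one-arm figure could be tempting to cite.

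**Working it through.** The documents give no scale, target, background rate or expected value for goal attainment, so there is no figure to reproduce. The check is whether the quantity can carry the stated interpretation.

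**Step 1: inputs.** From Measures: SHE women only, at 3 and 6 months, scored on their own plan. From Study Procedure: goals are chosen by the woman, optional and revisable. From the control description: no plan. Not in the documents, hence assumed: the background attainment *b*, meaning the share who would reach such goals without SHE.

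**Step 2: identification.** Write attainment in SHE women as *A* = *b* + *e*, where *e* is the SHE effect. The study observes *A*. It does not observe *b*, because no control woman has a goal to score. One observed quantity cannot fix two unknowns. A larger sample narrows the interval around *A* but does not help to separate *b* from *e*.

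**Step 3: illustration.** Take an observed *A* of 60% and solve *e* = *A* - *b*:

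| Assumed background *b* | Implied SHE effect *e* |
|---|---|
| 20% | 60 - 20 = +40 points |
| 40% | 60 - 40 = +20 points |
| 60% | 60 - 60 = 0 points |
| 70% | 60 - 70 = -10 points |

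The same result fits a large benefit, no effect or slight harm.

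**Step 4: how often an inert SHE would look good.** Suppose *e* = 0, each of 20 women either reaches her goal or does not, and at least half doing so (10 or more of 20) is called favourable. This cut-off is mine; the Protocol sets none. The binomial probability P(X ≥ 10), with *n* = 20 and success probability *b*, is 0.3% at *b* = 0.2, 24.5% at 0.4, 87.2% at 0.6 and 99.9% at 0.8. A favourable result with no effect thus ranges from very unlikely to almost certain, depending on a rate that nobody will have measured.

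**The case against.** The strongest reply is that nothing in the plan depends on this measure. It has no threshold or test, it is not a named outcome, and a SHE-only process measure is natural in a treatment-development pilot whose main goal is feasibility and acceptability. The proper comparisons are already planned, and the SAP says that the study is not primarily one of hypothesis testing. All of this stands, and it limits the severity. It does not rescue the clause, which still draws a causal reading that the design cannot support.

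A reader might also infer more than the documents allow:

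- *That attainment would look favourable with no SHE effect.* This depends on the unknown background rate. At a low rate it would not (0.3% at *b* = 0.2 in the illustration). Only *can* is supported.
- *That keeping up a change is an easy goal.* No rate is given, and the Overview and Background describe these women as at high risk of relapse.
- *That only women willing to set a goal are counted.* The measure goes to women who took part in SHE; how a woman with no goal is scored is not stated.
- *That the pilot will present this figure as evidence of efficacy in its next application.* The Phase III section refers to the study's results in general and does not mention this measure.

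**Conclusion.** The point holds as a matter of interpretation. Goal attainment in SHE women alone does not identify any effect of SHE, and it can look favourable when there is none. In the illustration, one observed value of 60% is compatible with effects from +40 to -10 points over assumed background rates of 20% to 70%. Those rates are assumptions, but the lack of identification does not depend on them: it follows from the absence of a control or baseline value.

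Severity is minor. No planned estimate, test, sample size or decision uses the measure. The defect is confined to one clause, and correcting it changes only what may be concluded from the figure.

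**What to change.** In the Measures section of the Protocol, replace the clause on impact with: *a descriptive process measure of goal pursuit among SHE women; it will not be used as evidence of SHE impact.* Report alongside it the number of SHE women who set no goal.

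Rest statements of impact only on the SHE-control effect sizes with 95% confidence intervals already planned in Data Analysis and the SAP: using days (Timeline Follow-Back), service days (Treatment Services Review) and severity of partner violence (Composite Abuse Scale). Note that these do not cover every goal. Free-text goals, speaking to shelter staff and planning to attend partner-violence support groups fall outside substance use days and substance use services.

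The cost is one sentence and one count in the results, with no new data or visits. The downside is that one SHE-only figure can no longer be cited as evidence of effect.

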**Table 1: Schedule of Assessments:**

Measure	Intake	Post intervention and booster	3-months after shelter discharge	6 months after shelter discharge
Demographics	X			
Timeline Followback	X		X	X
Hair Sampling Testing			X	X
Breath Alcohol Testing			X	X
Urine Drug Screening			X	X
The Composite Abuse Scale	X		X	X
Safety Behavior Checklist	X		X	X
Treatment Services Review	X		X	X
Client Satisfaction Questionnaire		X		
Satisfaction with CIAS Software Scale		X		
Readiness Ruler	X		X	X

Confidence Ruler	X		X	X
Cyber Stalking Scale	X		X	X

**Retention**

The PI has had high retention rates (+ 85%) in treatment trials involving difficult-to-follow populations (e.g., substance using women with interpersonal violence and women with IPV). Furthermore, our prior research with battered residents leaving shelter, our follow up rates have been 82% retention at 6 months post-shelter and 80% at 9 months post shelter. The current study will employ several approaches that we have found helpful in achieving these low attrition rates, including staff’s strong relationships with participants, efforts to value and appreciate the women’s participation in the study, and frequent personal contact with the women for the duration of the study. Research staff calls women to remind them of their appointments and maintain a list of two other people who will always know where the participant resides. We can contact the women through private message on Facebook via a generic Facebook page of “She A. Smith” with no information about who we are or what we do. [name] has used this retention strategy safely and successfully in a study of women residents of a battered women’s shelter in Ohio. Transportation is provided as deemed necessary to complete assessments. Further, compensation for participants’ time for assessments helps facilitate retention. Finally, Rhode Island’s small size and population stability (residents rarely move out of state) also facilitate participant retention.

**Limitations**

The limitations of this study include: potential issues related to disclosure of sensitive information, the use of self-reports, assessment reactivity and effect on measured outcomes, the inclusion of only English-speaking participants, and generalizability of study results to other substance using populations.

**Potential risks**

There are four potential low- to moderate-risks to subjects associated with this research project:

**Breach of confidentiality:** Assessment procedures could reveal sensitive information about participants’ substance use and history of IPV. Risk of breach of confidentiality is possible, though highly unlikely. Specifically, if a participant tells research staff that she is planning to harm herself or her children, the research staff will report this information to the appropriate agency, as required by law. Other than the need to report those incidents that are regulated by mandatory reporting laws, we feel that there is minimal risk to participants with regard to other breaches in their confidentiality.

**Coercion:** Coercion occurs when potential participants feel compelled to participate in research for reasons such as perceived demand or the availability of large sums of reimbursement. This can be particularly true when there is little benefit to the individual for their participation (not an issue in this study). In the present study, the inclusion of a protected population and protection from coercion is of the utmost importance

**Discomfort:** Participation in the study may lead to psychological distress due to the sensitive nature of questions regarding disclosure of IPV and substance use and the related negative social and psychological consequences.

**Study-related partner violence:** Participants who return to or continue to have contact with their abuser may be at increased risk for abuse if he or she were to find out about the woman’s participation in the research project.

**Social or legal consequences:** Possible social or legal consequences due to revelations of IPV.

## **Adequacy of protection against risks**

At each point of contact in the studies, participants will be reminded of the alternative of not participating in the study (or once enrolled, to discontinue participation), and will be informed that their care at the Women's Center, Sojourner House, New Hope, or Battered Women's Shelter of Summit and Medina Counties, and any other follow-up care will in no way be affected by their decision to participate or not to participate in the study. Moreover, we will provide referral information to all participants at each point of contact. Further procedures to minimize each of these risks are described below.

*Recruitment and informed consent:* Shelter staff will inform research staff as new residents are admitted to the shelter. The RA will attend house meetings and schedule times to be at the shelters when new residents are available and will provide a description of the initial study phase, the screening phase (phase A). Shelter residents will be recruited to participate in a computer-based survey to help battered women be healthy. Women who are interested in participating in the screener will receive an information sheet, which will be summarized (and read for those who prefer this) in a private setting. The information sheet (used to protect anonymity of those who did not qualify or chose not to participate in the full study) will indicate that the purpose of screening is to find women who may be eligible for a study on health risk factors and will describe what is involved with participating in the study. Those women who verbally agree to participate will complete the 10-minute screener (there will be no identifiers at screening) using the CIAS software delivered on an easy to use, ultraportable Tablet PC. Women meeting study screening criterion (i.e., endorse substance use in the three months prior to shelter stay) will be given the opportunity to provide informed consent for the clinical trial, in a private setting. Research staff will carefully explain all aspects of the study to a potential recruit, including the risks and benefits and obtain participants' written informed consent. Recruits will be informed of the intervention commitment, amount and general types of assessments, and the follow-up procedures. The research assistant will orally describe the material written in the informed consent document and answer any questions the participant may have. Participants will be reminded that they are not required to participate in the study and that they will receive the standard care provided by the Women's Center, Sojourner House, New Hope, or Battered Women's Shelter of Summit and Medina Counties regardless of whether or not they choose to participate. Participants who give their consent will sign a copy of the document and will be given a signed copy of the informed consent document. Women who refuse to participate in the clinical trial will be provided referral information.

The use of computer technology for gathering self-report data further enhances overall protection. Data will be encrypted in transit between user and server. Importantly, no identifying information will be entered into the ACASI. Given the sensitive nature of this research, the computer software will simply generate a code number for each participant. Additionally, all forms with participant information will be marked with a code number and not with the participants' name. The PI will keep the link between the participant code number and name under lock-and-key. Any information about a participant will never be released to outsiders without their explicit consent, except in the event of abuse of children/elderly/handicapped (report to the State of Rhode Island) or a medical emergency, when pertinent medical information will be given to the medical personnel caring for the individual.

## **Protection against risk**

We will take the following steps to protect against risks associated with this research project:

*We will minimize the risk of breach of confidentiality.*

A Certificate of Confidentiality will be obtained from the National Institutes of Health prior to the commencement of research. The purpose of this certificate is to protect the identity of research subjects participating in studies that collect sensitive information. Potential participants

will be informed that a Certificate of Confidentiality has been obtained for this project and that this certificate will protect the investigators from being forced to release any research data in which participants can be identified, even under court order or subpoena, although this protection is not absolute. Potential participants will be informed of the situations in which they may not be protected under the Certificate of Confidentiality. No information about participants will be released without their permission or where required by law. [name] has successfully used this approach in previous studies involving substance using women and women with intimate partner violence (IPV).

Possible distress due to sensitive items will be noted clearly in the informed consent information sheet (for screening) and in the written informed consent form (for participants). All participants will be told that they can skip any question or quit at any time if they become uncomfortable. Moreover, clinical backup will be provided during all assessments and during the intervention phase of the study by a licensed clinician to help facilitate any stabilization and referral process for participants who decompensate during assessment procedures. The need for additional services will also be monitored during all follow-up assessments.

To further address possible distress due to sensitive items, participants will be asked by the computer program if anything the computer has asked or done is making them feel upset right now. The computer program will notify the research team at completion of the screening, intervention session, or assessment, if any participant answers yes to this question. (Note that the computer program will not provide details regarding any answers, only that there is a need to follow-up with the participant verbally to evaluate the need for assistance). At a minimum, all participants indicating some distress will be given a list of referral options. For the duration of the study, women who report significant homicide or suicide risk will be immediately referred for evaluation for psychiatric admission at a local emergency department and if in the shelter, the appropriate staff will also be notified. All research personnel (i.e., interventionists, research assistants) will be trained in the protocol for homicidal or suicidal risk and research procedures for these situations. A licensed clinician will be available at all times by pager. Research staff will contact the licensed clinician if there are any safety concerns.

*Suicide or homicide risk:* All subjects will be closely monitored for significant suicidal and homicidal risks. During any phase of the study, if study interventionists, supervisors, or research staff judge that a subject is a significant suicide risk, the subject will be evaluated immediately by emergency room clinical staff at the closest hospital. If a subject reports active suicidal or homicidal ideation or plan during the SHE booster session, they will be evaluated individually by the study interventionist. If the suicidal or homicidal plan warrants immediate action, the interventionist will initiate voluntary or involuntary hospitalization. A licensed clinician will be available at all times by pager. Research staff will contact the licensed clinician if there are any safety concerns.

*Referrals for additional care:* All participants screened will receive a standard health information brochure with further information and resources on the health topics mentioned in the screening survey including a list of local substance use treatment referrals and community resources. Likewise, all participants who consent for the open trial or RCT study will receive a list of appropriate substance use treatment referrals and community resources. At any follow-up assessment, any participant who reports heavy drinking or the use of any illegal substances will be referred to appropriate treatment. Likewise, at follow-up assessments, any participant who reports current intimate partner violence (IPV) will be provided with information on IPV and a list of local IPV resources.

*We will minimize the risk of study-related partner violence.* Participants who return to or continue to have contact with their abuser may be at increased risk for abuse if he or she were to find out about the woman's participation in the research project. The measures suggested by Sullivan and Cain (2004) will be taken to maximize participant safety throughout the research. All phone calls will go through a confidential research line where the number is blocked. This line is answered, "Women and Infants Program," and partner violence is never mentioned.

Details of the research are not provided to anyone other than the actual participant. During each contact, participants will first be asked if it is a safe time to speak. Safe contact for follow-up assessments will be negotiated at each stage of the research. Both written and verbal contacts will be vague and never mention that the research involves partner violence. Follow-up interviews will be scheduled at a safe location. Safety plans will be negotiated up front (e.g., code words, cover story for reason for interview) if ever the abuser were to interrupt a phone call or assessment. Any handouts with important information (e.g., hotline numbers) will be available in wallet size copies without any reference to the study or name of organization. Participants' safety contact information will be updated monthly to determine if the contact information they previously provided is still accurate and safe. Participants will be given contact information for the research team and asked to let us know if the contact information they provided is no longer safe. All research personnel (i.e., interventionist, research assistant) will be able to call the PI for advice on any case where there is a concern for the safety of the respondent and the PI will be available at all times by pager.

Although the proposed intervention seeks to help a woman to develop strategies for keeping herself safe, it is possible that a woman who participates in the study might be at increased risk of partner violence because of increased assertiveness. At each follow-up assessment, our assessment of community resource use will ask about participants' visits to emergency rooms, health professionals, etc. The Composite Abuse Scale (CAS) will be administered to monitor abusive experiences in the context of a woman's relationship since the last assessment. Women will be asked at follow up assessments (3- and 6-month) about any occurrences of hospitalizations for medical, psychiatric, or substance use issues or emergency room visits, and whether or not any of these events were related to IPV in order to better gather information regarding any potential serious adverse events. These events will be reported to the Data Safety Monitoring Board (DSMB).

For the duration of the study, if a woman discloses that she is in an abusive relationship, she will be provided with the battered women's crisis line for emergencies, referrals to battered women's shelters, and told how to obtain a restraining order. If the partner of the participant is also abusing her children, the research staff person involved will let the woman know that she as the mother is responsible for protecting her children and if her partner hurts them and she fails to call child welfare or the police, she could be charged with neglect and her children could be taken away. The research staff will encourage the woman to call child welfare herself as child welfare is more likely to view the woman favorably under these circumstances. The research personnel involved will provide the woman with the relevant phone number/s. The research personnel involved will let the woman know that she will be calling child welfare herself because it is the law. This same procedure will be followed for any other case of suspected child abuse.

